10.10.3. Objectives, Estimands, and Endpoints for Russian Cohort

Safety Objective	Estimands	Safety Endpoints
To describe the safety profile of 20vPnC	
In participants (primary study population and Russian cohort combined) receiving at least 1 dose of investigational product and having safety data reported after any vaccination in each vaccine group:
 
 • The percentage of participants reporting prompted local reactions within 7 days after each vaccination • The percentage of participants reporting prompted systemic events within 7 days after each vaccination • The percentage of participants reporting AEs from Dose 1 to 1 month after Dose 2 and from Dose 3 to 1 month after Dose 3 • The percentage of participants reporting SAEs through 1 month after Dose 3 • The percentage of participants reporting NDCMCs through 1 month after Dose 3 	
 • Prompted local reactions (redness, swelling, and pain at the injection site) • Prompted systemic events (fever, decreased appetite, drowsiness/increased sleep, and irritability) • AEs • SAEs • NDCMCs
Primary Pneumococcal Immunogenicity Objective	Estimands	Primary Pneumococcal Immunogenicity Endpoints
To describe the IgG responses induced by 20vPnC in the Russian cohort	
In evaluable Russian participants for each of the 20 serotypes in 20vPnC for each vaccine group:
 
 • Percentages of participants with predefined IgG concentrations at 1 month after Dose 2 • IgG GMCs at 1 month after Dose 2 • IgG GMCs at 1 month after Dose 3 	
 • Pneumococcal IgG concentrations • Pneumococcal OPA titers
Secondary Pneumococcal Immunogenicity Objective	Estimands	Secondary Pneumococcal Immunogenicity Endpoints
To further describe immune responses induced by 20vPnC in the Russian cohort	
In evaluable Russian participants for each of the 20 serotypes in 20vPnC for each vaccine group:
 
 • Percentages of participants with predefined IgG concentrations at 1 month after Dose 3 • OPA GMTs at 1 month after Dose 2 • OPAs GMTs at 1 month after Dose 3 	
 • Pneumococcal IgG concentrations • Pneumococcal OPA titers

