Dose 3 evaluable immunogenicity	
Any participants who
 
 1. Are eligible and randomized, 2. Are within the protocol-defined age window (ie, 42-112 days of age, inclusive) on the day of Dose 1, 3. Receive all 3 vaccinations as randomized, with Dose 3 received within the protocol-defined window (ie, 335-386 days of age, inclusive), 4. Have at least 1 valid immunogenicity result within 27 to 56 days, inclusive, after Dose 3, and 5. Have no other major protocol deviations as determined by the clinician. 
The Dose 3 evaluable immunogenicity population will be the primary analysis population for pneumococcal immunogenicity results after Dose 3.
 
The statistical analysis of concomitant immunogenicity results 1 month after Dose 3 will be primarily based on the Dose 3 evaluable immunogenicity populations restricted to those who also receive the appropriate concomitant vaccines at the Dose 3 visit.
 
Participants will be grouped according to their randomized vaccine in the immunogenicity analysis.

Population	Description
Safety	
All participants who receive at least 1 dose of the investigational product and have safety data assessed after any dose. Participants will be grouped according to the vaccine as administered in the safety analysis.
 
Safety data after Dose 3 will be summarized for participants in the safety population who receive Dose 3 with safety follow-up after Dose 3.

For the Dose 2 and Dose 3 evaluable immunogenicity population definitions, the blood collection window has been expanded by 1 extra day before and 14 days after the protocol-specified blood collection window of 28 to 42 days defined in the protocol, for consistency with established rules in the 13vPnC development program. The major protocol deviations will be determined by clinical review or medical monitor. A major protocol deviation is a protocol deviation that, in the opinion of the sponsor's clinician, would materially affect assessment of immunogenicity, eg, participant receipt of a prohibited vaccine or medication that might affect immune response or a medication error with a suspected decrease in potency of the vaccine. The sponsor's clinician will identify those participants with major protocol deviations before any unblinded analysis.

Local reactions and systemic events based on the e-diary will be summarized from participants with any e-diary data reported in the safety population.

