6. ANALYSES AND SUMMARIES

Unless otherwise specified, the analyses and summaries are based on the primary study population. The analyses and summaries on the Russian cohort will be described separately in Section 9, [Appendix 2](#).

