6.5.1.2. Medical History

Each reported medical history term will be mapped to a SOC and preferred term according to MedDRA. The number and percentage of participants with an assigned vaccine having at least 1 diagnosis, overall and at each SOC and preferred term level, will be summarized by vaccine group and overall by cohort for the overall safety population.

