7.2. Analysis Timings

The safety and immunogenicity results in this study will be analyzed and reported when the safety and immunogenicity data 1 month after Dose 3 are available from all participants in the primary study population.

The safety and pneumococcal immunogenicity results of the Russian cohort will be analyzed and reported when safety and pneumococcal immunogenicity data are available from all participants in the Russian cohort.

Sponsor personnel involved in evaluating participant data in the primary study population will be blinded to vaccine assignment in that population until the analysis at the completion of the primary study population. The study team will remain blinded to the vaccine assignments of the Russian cohort until that cohort has completed the study. Laboratory personnel performing the assays will remain blinded until all assays are completed and assay results of each population/cohort are finalized.

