Appendix 2. Analysis for the Russian Cohort

Objectives, Estimands, and Endpoint for the Russian Cohort

Safety Objective	Estimands	Safety Endpoints
To describe the safety profile of 20vPnC in the Russian cohort	
In Russian participants receiving at least 1 dose of investigational product and having safety data reported after any vaccination in each vaccine group:
 
 The percentage of participants reporting prompted local reactions within 7 days after each vaccination The percentage of participants reporting prompted systemic events within 7 days after each vaccination The percentage of participants reporting AEs from Dose 1 to 1 month after Dose 2 and from Dose 3 to 1 month after Dose 3 The percentage of participants reporting SAEs through 1 month after Dose 3 The percentage of participants reporting NDCMCs through 1 month after Dose 3 	
 Prompted local reactions (redness, swelling, and pain at the injection site) Prompted systemic events (fever, decreased appetite, drowsiness/increased sleep, and irritability) AEs SAEs NDCMCs
Primary Pneumococcal Immunogenicity Objectives	Estimands	Primary Pneumococcal Immunogenicity Endpoints
To describe the IgG responses induced by 20vPnC in the Russian cohort	
In evaluable Russian participants for each of the 20 serotypes in 20vPnC for each vaccine group:
 
 Percentages of participants with predefined IgG concentrations at 1 month after Dose 2 IgG GMCs at 1 month after Dose 2 IgG GMCs at 1 month after Dose 3 	
 Pneumococcal IgG concentrations
Secondary Pneumococcal Immunogenicity Objectives	Estimands	Secondary Pneumococcal Immunogenicity Endpoints
To further describe immune responses induced by 20vPnC in the Russian cohort	
In evaluable Russian participants for each of the 20 serotypes in 20vPnC for each vaccine group:
 
 Percentages of participants with predefined IgG concentration at 1 month after Dose 3 OPA GMTs at 1 month after Dose 2 OPA GMTs at 1 month after Dose 3 	
 Pneumococcal IgG concentrations Pneumococcal OPA titers

After the final data from the Russian participants become available, a separate analysis based on the Russian cohort will be conducted. The analysis methods will be similar to the analysis conducted for the primary study population, except that:

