- Only descriptive statistics will be displayed.
- The evaluable immunogenicity population definitions for the Russian cohort are similar to that for the primary study population ([Section 4](#)), with the exception that the protocol defined age window for Dose 1 is 42 to 70 days, inclusive, and for Dose 3 is 335 to 455 days, inclusive.

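### Is it unsettled whether Russian infants' safety data are pooled with the primary population or reported alone?

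*Protocol*

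**What the plan says.** Protocol Sections 3 and 9.1.1 send the reader to 10.10.3 for the Russian estimands. The safety row there begins "In participants (primary study population and Russian cohort combined) receiving at least 1 dose of investigational product" and lists five percentages: local reactions, systemic events, AEs, SAEs and newly diagnosed chronic conditions. The two immunogenicity rows of the same table are confined to evaluable Russian participants.

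Elsewhere the protocol keeps the cohort apart. The synopsis, 9.4.3 and 10.10.1 each call for a separate descriptive summary. Sections 4.1 and 4.2 exclude the cohort from the primary population and place its results in a supplemental report.

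SAP Appendix 2 restates the five percentages "In Russian participants receiving at least 1 dose of investigational product and having safety data reported after any vaccination in each vaccine group". On methods it says: "The analysis methods will be similar to the analysis conducted for the primary study population, except that" two exceptions hold. Output is limited to descriptive statistics, and the age windows change: "The evaluable immunogenicity population definitions for the Russian cohort are similar to that for the primary study population", apart from those windows.

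SAP Section 4 defines a single safety set with no cohort restriction: "All participants who receive at least 1 dose of the investigational product and have safety data assessed after any dose". SAP Section 6 sets a default, "Unless otherwise specified, the analyses and summaries are based on the primary study population", and its next sentence moves Russian analyses to Appendix 2. Inside Section 6, 6.5.1.2 says medical history "will be summarized by vaccine group and overall by cohort for the overall safety population". SAP 7.2 adds: "The study team will remain blinded to the vaccine assignments of the Russian cohort until that cohort has completed the study".

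On adverse-event tiers, the protocol synopsis applies the 3-tier approach to the primary study population. SAP 3.1.1.4 sets the Tier 2 cut at 1% of participants in at least one group.

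**The concern.** Read on its own, the table meant to define Russian-specific estimands contains no Russian-only safety estimand. A programmer working from the protocol would build about 630 infants per group, and one working from SAP Appendix 2 would build about 30. A difference in Russian infants would hardly show in the pooled set.

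The SAP seems to add two loose ends. The medical-history table could cover 1200 or 1260 infants. If it included Russian infants split by vaccine group at the primary analysis, it would break the blind that SAP 7.2 protects. Appendix 2 also does not say whether the tier rule, and the between-group intervals attached to Tier 2, carry over to a cohort of 60. What would be at stake is the denominator of the Russian safety tables and the content of one baseline table.

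**Working it through.** **Inputs.** Primary population about 1200, randomised 1:1, so 600 per group (Protocol 4.1, 4.1.2, 9.2.3). Russian cohort about 60, 1:1, so 30 per group (Protocol 10.10.1). Combined: 1260, or 630 per group. I assume enrolment as planned, with every infant in the safety set.

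**1. The plan's own safety figure.** Table 7 follows from P(at least 1 event) = 1 − (1 − p)^n with n = 600. For p = 0.1%, 0.2%, 0.3%, 0.4% and 0.5% this gives 45.1%, 69.9%, 83.5%, 91.0% and 95.1%, matching all five rows. The stated safety sample size therefore rests on the primary population alone, and neither reading of 10.10.3 alters it.

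**2. What pooling would do.** The Russian share is 60/1260 = 4.76% = 1/21. Pooled rate − primary rate = (Russian rate − primary rate)/21. As an illustration, take 20% in the primary population and 40% in Russian infants: (600 × 0.20 + 30 × 0.40)/630 = 132/630 = 21.0%. The pooled table would be nearly the primary table again.

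**3. What each reading can show at a true rate of 0.4%.** With n = 630 the chance of at least one event is 92.0%, against 91.0% at 600. With n = 30 it is 11.3%. With no events, the two-sided 95% Clopper-Pearson upper limit is 1 − 0.025^(1/n): 0.58% at 630 and 11.6% at 30. The two readings are very different tables, so it matters that the analyst has a clear instruction.

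**4. Is there one? The texts side by side.**

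| Place | Safety set for Russian data |
|---|---|
| Protocol synopsis, 9.4.3, 10.10.1 | Separate |
| Protocol 10.10.3, safety row | Combined with primary |
| SAP Appendix 2 | Russian only |
| SAP Section 6, opening | Primary by default; Russian analyses in Appendix 2 |

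Protocol Section 9 and SAP Section 2 let the SAP modify the protocol. Both require an amendment only for major changes to primary endpoint definitions or their analyses. The 10.10.3 row is headed as a safety objective, not a primary one, and is descriptive. The primary safety objective in Protocol Section 3 is unaffected, and SAP Table 2 is titled for the primary study population. Appendix 2 therefore governs, and it agrees with every protocol passage except the one row.

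**5. Medical history.** SAP 6.5.1.2 falls under the Section 6 default and does not mention Russian infants. The demographics summary just before it is by vaccine group and overall, with no cohort split. SAP Section 7 and 7.2 schedule the Russian analysis after that cohort finishes. A by-group Russian column at the primary analysis is thus ruled out by the blinding rule itself, which leaves the primary population.

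**6. Tiers.** The 1% cut is 6 of 600. It is 7 of 630 (0.01 × 630 = 6.3) and 1 of 30 (0.01 × 30 = 0.3). One infant in 30 is 3.3%, so in a Russian-only table every reported term would pass and the tiers would sort nothing. The synopsis applies tiers to the primary population, and Appendix 2 limits Russian output to descriptive statistics. In Protocol 9.4.2 the descriptive statistics for reactogenicity are counts, percentages and Clopper-Pearson intervals, with between-group differences listed as an addition.

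**The case for a change.** The strongest case is that 10.10.3 is no stray remark, since two other sections name it as the home of the Russian estimands. Its safety objective omits any mention of the Russian cohort while the rows below include it, so a pooled display may have been intended. The SAP does not say that it departs from the protocol. It is version 1, dated three days after Amendment 2, with an empty change log. Pooling would also mix schedules that the protocol itself gives as a reason for keeping the cohort apart: Dose 2 at 60 to 90 versus 42 to 63 days after Visit 1, and Dose 3 up to 455 versus 386 days of age.

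The conflict between that row and the other passages stands, and the combined estimand has no matching output in the visible SAP. It does not follow that the analyst lacks a rule. If a pooled display was intended, its absence costs a descriptive table that differs from the primary one by 1/21 of the Russian-primary gap. The argument about mixed schedules supports the separate analysis that Appendix 2 already plans.

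On medical history, the default does yield where something else is specified, but a loose *by cohort* in a baseline table is weak evidence of an exception. On tiers, SAP 5.2.1 counts 95% intervals, where applicable, among descriptive statistics for categorical data. The text therefore does not strictly exclude Tier 2 between-group intervals for the Russian cohort. That leaves open whether one column is printed in a descriptive table.

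**Conclusion.** No change follows. The combined wording in Protocol 10.10.3 is a real but isolated inconsistency, and the SAP's Russian-only plan already decides what will be produced. The wording in SAP 6.5.1.2 reads as a leftover, and the silence on tiers is detail that the synopsis and the descriptive-only limit largely supply. Aligning the texts would alter no noninferiority test, no Table 7 probability, no primary safety percentage and no Russian-only percentage. The largest numerical effect of the alternative reading is a pooled rate shifted by 1/21 of the Russian-primary difference, in a table the visible SAP does not call for.

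This rests on planned enrolment (1200 and 60, each 1:1), on all infants entering the safety set, and on the visible text. Parts of the SAP between 6.2.2 and 6.5 are blacked out, so the absence of a combined output or of a further population definition can be stated only for what can be read.

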10.10.4. Notes on the Russian National Immunization Program

The following table includes information about the National Immunization Schedule of the Russian Federation for children 0 through 18 months of age:

NATIONAL IMMUNIZATION SCHEDULE (Partial)⁷⁵ List of amending documents (as amended by Orders of the Ministry of Health of Russia No. 370H dated 16 June 2016, No. 175H dated 13 April 2017, No. 243H dated 24 April 2019, No. 967H dated 14 September 2020)	
Categories and age of citizens subject to compulsory vaccination	Immunization name
Newborns in the first 24 hours of life	First vaccination against hepatitis B virus ^a
Newborns, on the 3rd - 7th day of age	Vaccination against tuberculosis ^b
Children of 1 month of age	Second vaccination against hepatitis B virus ^a
Children of 2 months of age	Third vaccination against hepatitis B virus (risk groups) ^c
	First vaccination against pneumococcal infection
Children of 3 months of age ^d	First vaccination against diphtheria, pertussis, tetanus
	First vaccination against poliomyelitis ^e
	First vaccination against Haemophilus influenzae (risk groups) ^f
(as amended by Order of the Ministry of Health of Russia of No. 175H dated 13 April 2017)	
Children of 4.5 months of age ^d	Second vaccination against diphtheria, pertussis, tetanus
	Second vaccination against Haemophilus influenzae (risk groups) ^f
	Second vaccination against poliomyelitis ^e
	Second vaccination against pneumococcal infection
(as amended by Order of the Ministry of Health of Russia of No. 175H dated 13 April 2017)	

NATIONAL IMMUNIZATION SCHEDULE (Partial)⁷⁵	
List of amending documents	
(as amended by Orders of the Ministry of Health of Russia No. 370H dated 16 June 2016, No. 175H dated 13 April 2017, No. 243H dated 24 April 2019, No. 967H dated 14 September 2020)	
Categories and age of citizens subject to compulsory vaccination	Immunization name
Children of 6 months of age ^d	Third vaccination against diphtheria, pertussis, tetanus
	Third vaccination against hepatitis B virus ^a
	Third vaccination against poliomyelitis ^g
	Third vaccination against Haemophilus influenzae (risk group) ^f
(as amended by Order of the Ministry of Health of Russia of No. 175H dated 13 April 2017)	
Children of 12 months of age	Vaccination against measles, rubella, mumps
	Fourth vaccination against hepatitis B virus (risk groups) ^c
Children of 15 months of age	Revaccination against pneumococcal infection
Children of 18 months of age ^d	First revaccination against poliomyelitis ^g
	First revaccination against diphtheria, pertussis, tetanus
	Revaccination against Haemophilus influenzae (risk groups)
(as amended by Order of the Ministry of Health of Russia of No. 175H dated 13 April 2017)	

- a. First, second, and third vaccinations are carried out according to the 0-1-6 schedule (1st dose - at the start of vaccination, 2nd dose - one month after the 1st vaccination, 3rd dose - 6 months after the start of vaccination), with the exception of children belonging to risk groups, for whom the vaccination against hepatitis B virus is carried out according to the 0-1-2-12 schedule (1st dose - upon start of the vaccination, 2nd dose - one month after the 1st vaccination, 3rd dose - 2 months after the start of vaccination, 4th dose - 12 months after the start of vaccination).
- b. Vaccination is carried out with a tuberculosis vaccine for attenuated primary vaccination (BCG-M, ie, modified BCG vaccine); in the constituent entities of the Russian Federation with morbidity rates exceeding 80 per 100,000 population, as well as in the presence of tuberculosis patients in the environment of a newborn - a tuberculosis vaccine (BCG vaccine).
- c. Vaccination is carried out for children belonging to risk groups (born from mothers carrying HBsAg, HBV or who have had HBV in the third trimester of pregnancy, who do not have blood test results for hepatitis B markers, who use narcotic drugs or psychotropic substances, from families with a carrier of HBsAg or a patient with acute HBV and chronic viral hepatitis).
- d. Vaccination and revaccination of children at risk can be carried out with immunobiological drugs for immunoprophylaxis of infectious diseases, containing combinations of vaccines to be used at appropriate age periods.
(footnote introduced by Order of the Ministry of Health of Russia No. 175H dated 13 April 2017)
- e. First and second vaccinations are carried out with the polio vaccine (inactivated).
- f. Vaccination is carried out for children belonging to risk groups (with diseases of the nervous system, immunodeficiency disorders, or anatomical defects leading to a sharply increased risk of hemophilic infection; with intestinal malformations; with oncological diseases and/or receiving immunosuppressive therapy for a long time; children born to mothers with HIV infection; children with HIV infection; premature and low-birth-weight children; children in orphanages).
(footnote as amended by Order of the Ministry of Health of Russia of No. 243H dated 24 April 2019)
- g. Third vaccination and subsequent revaccinations of children against poliomyelitis are carried out with the polio vaccine (live); children belonging to risk groups (with diseases of the nervous system, immunodeficiency disorders, or anatomical defects leading to a sharply increased risk of hemophilic infection; with intestinal malformations; with oncological diseases and/or receiving long-term immunosuppressive therapy; children born to mothers with HIV infection; children with HIV infection; premature and low-birth-weight children; children in orphanages) - with the polio vaccine (inactivated).
(footnote as amended by Order of the Ministry of Health of Russia of No. 243H dated 24 April 2019)

The use of Infanrix hexa will provide the concomitant vaccine antigens of diphtheria, tetanus, acellular pertussis, hepatitis B, poliovirus, and *Haemophilus influenzae* type b (DTaP, HBV, IPV, and Hib) and be administered at approximately 2, 4.5, and 11 to 15 months of age with the blinded study vaccine (20vPnC or 13vPnC [control vaccine]). Although the administration of Infanrix hexa will be given on a slightly different schedule than the National Immunization Schedule of the Russian Federation noted above, numerous studies of Infanrix hexa have demonstrated that an immunization schedule of 2 infant doses and a toddler dose will provide protection against the diseases covered by the vaccine. Based on data in the Russian Infanrix hexa SmPC, the 2-dose and 3-dose primary vaccination schedules have similar overall seroprotective or seropositive antibody levels against each of the vaccine antigens.

Therefore, Infanrix hexa use in this study in accordance with a 2-dose primary and booster schedule is consistent with the manufacturer's label for providing appropriate and adequate protection of the infant against the aforementioned diseases.

